Rapid diagnosis and management of intra-abdominal hemorrhage after blunt trauma is critical in the triage and assessment of trauma patients (1). The Focused Assessment with Sonography in Trauma examination (FAST) is an efficient, bedside, non-ionizing, non-invasive method for assessing hemoperitoneum (the presence of blood in the peritoneal cavity), in traumatically injured patients. The FAST is taught during the Acute Trauma Life Support (ATLS) Course, and is the gold standard for the initial assessment of abdominal and chest trauma (2). FASTs have excellent specificity (94.7-99.6% in most series), however sensitivity is low (20-60%) (3-5). Improving the sensitivity of the FAST would allow for earlier detection and management of life-threatening intra-abdominal hemorrhage for innumerable trauma patients.

FASTs are typically performed with the patient in the standard position, lying flat on their back. The right upper quadrant (RUQ), left upper quadrant (LUQ) and suprapubic region are scanned and evaluated for hemoperitoneum. If fluid is found in any of these views, the patient is emergently taken to the operating room (OR) to treat the intra-abdominal hemorrhage.

It has been previously shown that a standard FAST is most likely to detect hemoperitoneum in the RUQ in Morison's pouch, the space on the right side of the body that separates the liver and the right kidney (hepatorenal recess) (2). A recent pilot by Pigneri et al., compared standard FAST exam to FAST exam after the patient had been rolled onto their right side; this modified evaluation method was termed Focused Assessment with Sonography in Trauma examination after Right sided roll (FASTeR). The rationale was this position likely uses gravity to collect intra-abdominal fluid into Morison's pouch, thus making it possible to visualize small volumes of fluid that would otherwise be undetectable when the patient is lying flat (6). This study demonstrated earlier identification of intra-abdominal fluid with the FASTeR when compared to the standard FAST (6).

Rationale

All patients are rolled onto one side or the other during normal trauma evaluation. Changing practice to turn the patient onto the right side for a modified FAST, or FASTeR, can potentially increase exam sensitivity without delaying care. Our goal is to perform a large, multicenter study to evaluate the impact of FASTeR versus the standard

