FAST in hemodynamically unstable trauma patients. We plan to prospectively collect data for creation of a multicenter database; enrolled subjects would undergo both the standard FAST and when appropriate (see Methods) a FASTeR. Our aim is to determine the sensitivity and specificity of the FAST and FASTeR, and determine which exam was more accurate in recognizing hemoperitoneum. Exam results will be confirmed with computed tomography (CT) imaging or operative findings.

Potential Risks and Benefits

Potential Risks

There are no expected medical risks to the study participants in excess of the normal risks of the FAST, which is minimal.

Potential Benefits

If the FASTeR is shown to detect small volumes of hemoperitoneum earlier than was previously possible with the FAST, patients may directly benefit from earlier diagnosis and treatment. Early identification of hemoperitoneum has been shown to be strongly correlated with increased survival rates (1).

Study Objectives

Primary Objective

To calculate and compare the sensitivity and specificity of detecting hemoperitoneum in the RUQ for the standard FAST and the FASTeR in the research subjects. Actual injury complex will be confirmed by CT or operative findings.

Secondary Objective

To calculate and compare the false positive rate, false negative rate, positive predictive value, negative predictive value, and positive and negative likelihood ratios for the standard FAST and FASTeR. Exam results for individual subjects will be compared to see if there is a significant difference in result accuracy.

Study Design

This is a prospective multicenter study. Detailed responsibilities for the lead (Memorial Regional Hospital) and satellite centers below.

Memorial Regional Hospital (lead)

- 1. Maintain database for enrolled MRH subjects. Data collected will include HIPAA identifiers (included in outcome measures) to monitor our own data integrity.
- 2. As lead center, MRH will aggregate and analyze collected data from satellite centers which will be submitted without HIPAA identifiers.
- 3. MRH to manage subjects meeting inclusion criteria according to our institutional patient management protocols.
- 4. MRH to adhere to IRB protocol and application as submitted.

Satellite Centers

- 1. Each center must apply and receive IRB approval from their respective IRB(s).
- 2. Each center is responsible for their own data integrity, as outlined in their approved IRB protocol and application.

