- 3. Each center to provide IRB outcome or waiver letter to the lead center.
- 4. Each center to complete the data sharing agreement specific to this study.
- 5. Each center to provide care according to their institutional patient management protocols.
- 6. Each center to submit de-identified data to the lead center for analysis.

Subject Selection

Inclusion Criteria

1. Patients over 18 and under 89 years of age who present as a trauma activation with clinical history or physical signs of blunt abdominal trauma and hemodynamic instability

Exclusion Criteria

- 1. Patients under 18 and over 89 years
- 2. Pregnant women
- 3. Patients with prohibitive right sided chest trauma
- 4. Patients in extremis undergoing salvage maneuvers (chest compressions or emergent surgical intervention) which prevents performance of an ultrasound examination
- 5. Patients who leave against medical advice or are otherwise removed from the medical system before their work up has been completed

Sample Size

50 participants at MRH and 250 participants total for all sites.

Research Design

This is a prospective multicenter study, where MRH will act as the lead center. Each contributing center is responsible for obtaining IRB approval and maintaining data integrity outlined in their approved IRB protocol and application from their respective institutions. Once IRB approval has been obtained, we will begin enrolling trauma patients prospectively into a registry. The participating centers for this study represent a diverse set of trauma centers and emergency departments and include institutions with varying trauma verifications (e.g. ACS and State), sizes, geographical/metropolitan locations, and resource availability to ensure inclusivity.

Since this is a prospective observational study, data will be collected prospectively without altering the manner in which the patients are managed by the surgeon and institution. Accordingly, an informed consent waiver is requested. Patients will be given a flyer with information about the study (see additional documents). Data will be collected for a two year period with interim analysis when specific enrollment targets are met. All data will be recorded on a data sheet and transferred to a secured database (REDCap) without patient identifiers.

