Patients with clinical history or physical signs suspicious for blunt abdominal trauma will undergo the standard FAST in the emergency department as per ATLS protocol. During the secondary survey, all patients are rolled for examination of their back and removal of the rigid spine board, per ATLS. In our study, we will standardize this practice so that all patients are rolled onto their right side for this portion of the examination. Patients with extensive right sided chest trauma will be excluded at the discretion of the Trauma Surgeon. After the right sided roll to remove the back board, a repeat ultrasound examination of the RUQ will be performed.

All participating centers, including MRH, will collect and submit the following data to the database for each enrolled subject: age, gender, initial trauma bay vital signs, mechanism of injury, results of the FAST, results of the FASTeR, and injury complex as confirmed by CT imaging or operative findings for their respective centers. Both the CT scan and any surgical intervention that the participant undergoes as a study subject will be performed through routine standard of care procedures. The database will not contain HIPAA identifiers

MRH will record our internal subject medical record numbers and dates of admission to verify data fields and monitor our own data integrity. All data will be de-identified prior to publication.

Study Outcome Measures (Endpoints)

The study outcome measures will be recorded using the "Multicenter Study: Can we be FASTeR? A multicenter study utilizing Right sided roll to improve sensitivity of the FAST examination" data collection form. The patient medical record number (MRN) will be

recorded by hand on the tool for all MRH enrolled subjects only; subject data will be cross-checked with the electronic records in order to maximize data integrity.

- 1. Number of patients admitted and discharged from MRH between the timeframe (October 16, 2017- October 16, 2019) who present as a trauma activation with clinical history or physical signs of blunt abdominal trauma and hemodynamic instability
 - a. MRN (recorded by hand), internal use only
 - b. Admission date (recorded by hand), internal use only
- 2. Demographics (e.g. age, gender)
- 3. Admission vital signs (e.g. heart rate [bpm], blood pressure, respiratory rate, oxygen saturation)
- 4. Results (positive or negative) of the FAST (RUQ, LUQ, surprapubic)
- 5. Results of the FASTeR (RUQ)

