- 6. Method where final injury complex determined (if applicable)
 - a. Operative findings
 - b. CT scans
 - c. Other imaging (e.g. MRI, x-ray, ultrasound)
- 7. Final injury complex (if applicable)
 - a. Liver injury
 - b. Splenic injury
 - c. Gastrointestinal injury (type)
 - d. Genitourinary injury (type)
 - e. Vascular/mesenteric injury (type)
 - f. Pancreatic injury
 - g. Other (type)
- 8. Outcome of hemoperitoneum confirmed by imaging or operative findings

Statistical Analysis Plan

All subjects who meet inclusion criteria and have complete data available will be used for data analysis. The sensitivity and specificity (with confidence intervals) for detecting hemoperitoneum using the standard FAST or the FASTeR versus the actual injury complex findings (CT or operative findings) will be calculated in the research subjects along with the false positive rate, false negative rate, positive predictive value, negative predictive value, and positive and negative likelihood ratios. A McNemar's test will be used to directly compare the accuracy of the FAST and FASTeR results for individual research subjects.

The data pooled from the participating centers will provide a robust data set that will minimize center or physician specific result bias and provide the needed statistical volume as calculated by the power analysis.

Study Procedures

Subject Identification, Recruitment, and Screening

This a prospective multicenter study, which will prospectively record data without altering the manner in which the patients are managed by the surgeon and institution. Accordingly, an informed consent waiver is requested. All data will be recorded on a data sheet and transferred to a secured database (REDCap) without patient identifiers.

Eligibility for study enrollment will be considered for all patients presenting to MRH as a trauma alert during the study period, with a clinical history or physical signs for blunt abdominal trauma who would clinically indicate a standard FAST in the trauma bay as per ATLS protocol. Patients with extensive right sided chest trauma will be excluded at the discretion of the Trauma Surgeon. Both the CT scan and any surgical intervention that the participant undergoes as a study subject will be performed through routine standard of care procedures.

Study Duration

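### The SAP names injury complex as the reference for a hemoperitoneum test, although the form records hemoperitoneum separately; the SAP should name that item and the RUQ view

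*Combined protocol and SAP*

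**What the plan says.** All references are to the combined protocol and SAP.

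- **Aim (Rationale).** The study is to "determine which exam was more accurate in recognizing hemoperitoneum".
- **Primary Objective.** It compares "sensitivity and specificity of detecting hemoperitoneum in the RUQ for the standard FAST and the FASTeR". The next sentence reads "Actual injury complex will be confirmed by CT or operative findings".
- **Secondary Objective.** It adds "false positive rate, false negative rate, positive predictive value, negative predictive value, and positive and negative likelihood ratios for the standard FAST and FASTeR".
- **Statistical Analysis Plan.** Sensitivity and specificity are computed "for detecting hemoperitoneum using the standard FAST or the FASTeR versus the actual injury complex findings (CT or operative findings". The secondary measures come from the same comparison. McNemar's test compares the accuracy of the two exams within subjects. Neither sentence mentions the RUQ.
- **Research Design.** The data that every center submits include "results of the FASTeR, and injury complex as confirmed by CT imaging or operative findings for their respective centers". Hemoperitoneum is not in that list.
- **Study Outcome Measures.** Item 4 records FAST in three views and item 5 records FASTeR in the RUQ only. Item 6 gives the method by which the injury complex was determined, and 6c allows other imaging, including ultrasound. Item 7 lists the injury complex organ by organ. Item 8 is hemoperitoneum, confirmed by imaging or at operation.
- **Study Duration.** The sample size assumes that FAST identifies up to 60% of subjects with significant intra-abdominal injury, and that FASTeR finds hemoperitoneum in 1 of 4 injured subjects whose FAST was negative.

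**The concern.** FAST and FASTeR look for free fluid. Organ injury and free fluid overlap but are different conditions, and the form treats them as different items. If the reference is organ injury, a subject with an injury and no fluid has nothing for ultrasound to see, yet counts as a miss by both exams. The published sensitivities would then mix fluid that was missed with fluid that was never there. NPV and the likelihood ratios inherit the same error.

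The wording is not a single slip. The Primary Objective and the Research Design list use the same term, and Study Duration counts injured subjects. An analyst at the lead center who pools data from many sites would find no written instruction to use item 8.

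A smaller point concerns the view. The Primary Objective sets an RUQ comparison, but the SAP does not repeat it, while the form holds three FAST views and one FASTeR view.

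**Working it through.** **Inputs.** The total of 250 comes from Sample Size ("50 participants at MRH and 250 participants total for all sites"). Specificity of 97% is chosen from within the 94.7-99.6% given in the opening background text. Sensitivities of 60% and 70% borrow the Study Duration figures (0.60 + 0.25 × 0.40 = 0.70). They are used here only as illustrative values against hemoperitoneum, because the plan does not make their denominator clear.

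Assumed, not in the document:
- hemoperitoneum prevalence of 20%;
- f, the share of injured subjects who have no free fluid, at 10-30%;
- no scan-positive subjects in that share;
- every hemoperitoneum case has a listed injury.

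The plan states no figure for f or for prevalence, so it has no figure of its own to reproduce on this point. The sample size of 209 does not enter.

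**Base table (reference = hemoperitoneum).** H = 0.20 × 250 = 50 cases and 200 non-cases. TN = 0.97 × 200 = 194 and FP = 6.
- FAST: TP 30, FN 20, NPV = 194/214 = 90.7%, LR- = 0.40/0.97 = 0.41.
- FASTeR: TP 35, FN 15, NPV = 194/209 = 92.8%, LR- = 0.30/0.97 = 0.31.

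**Change of reference to injury.** The injured number H/(1-f), so x = Hf/(1-f) subjects move from TN to FN for both exams. Then:
- Se' = Se × (1-f), and the difference is also multiplied by (1-f);
- NPV' = (TN - x)/(TN + FN);
- Sp' = (TN - x)/(TN - x + FP);
- LR-' = (1 - Se')/Sp'.

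At f = 20%: x = 50 × 0.2/0.8 = 12.5. For FAST, Se' = 30/62.5 = 48.0%, NPV' = 181.5/214 = 84.8%, Sp' = 181.5/187.5 = 96.8% and LR-' = 0.52/0.968 = 0.54.

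| f | x | Se FAST / FASTeR (%) | Gain (points) | NPV FAST / FASTeR (%) | LR- FAST / FASTeR | Specificity (%) |
|---|---|---|---|---|---|---|
| 0 | 0 | 60 / 70 | 10 | 90.7 / 92.8 | 0.41 / 0.31 | 97.0 |
| 10% | 5.6 | 54 / 63 | 9 | 88.1 / 90.2 | 0.47 / 0.38 | 96.9 |
| 20% | 12.5 | 48 / 56 | 8 | 84.8 / 86.8 | 0.54 / 0.45 | 96.8 |
| 30% | 21.4 | 42 / 49 | 7 | 80.6 / 82.6 | 0.60 / 0.53 | 96.6 |

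The sensitivity columns do not depend on prevalence or specificity. NPV does: at 30% hemoperitoneum, FAST NPV goes from 85.0% to 80.8, 75.6 and 68.9%.

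**McNemar's test.** The moved subjects are negative on both exams. They change from both correct to both wrong, so they stay concordant. Under these assumptions the discordant counts do not change at all. In practice a few injured subjects without fluid may scan positive on one exam, so little affected is the right description.

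**View.** Let F be three-view FAST sensitivity and s the share of FAST true positives seen only outside the RUQ (not given in the plan). RUQ-only FAST sensitivity is F(1-s). If three-view FAST were entered against RUQ-only FASTeR, the gain would differ from the RUQ-to-RUQ gain by F × s. For s = 5, 10 and 20% that is 1, 2 and 4 points at F = 20%, and 3, 6 and 12 points at F = 60%.

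**The case against.** The strongest defense is that the term is used loosely. The SAP sentence is about detecting hemoperitoneum and points to CT or operative findings, which would show fluid as well as injury. Item 7 applies only where applicable and carries no present/absent rule. Item 8 sits under the endpoints and is the only item that is directly a hemoperitoneum outcome. The authors may well intend item 8. This stands as far as intent goes, so the literal reading cannot be presented as what will happen. It does not remove the point, because the form separates the two items, the SAP names the wrong one, and other sections repeat the term.

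Four stronger readings are tempting, and the document does not support them.

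- *A reader might infer that three-view FAST will be compared with RUQ-only FASTeR.* The Primary Objective already fixes the RUQ for both exams. The SAP is silent on this, not in conflict, and the F × s figures apply only if that objective were ignored. The Secondary Objective carries no RUQ limit, so the rule there is open.
- *A reader might infer that satellites do not collect hemoperitoneum.* Item 8 is on the multicenter form. Its absence from the Research Design list calls for confirmation and does not show a gap.
- *A reader might rescale the Study Duration figures to hemoperitoneum cases by dividing by (1-f).* At f = 30% this gives 0.60/0.70 = 85.7% plus 0.10/0.70 = 14.3%, a FASTeR sensitivity of 100%. The 60% also equals the upper end of the FAST sensitivity range in the background text. The denominator is unclear, and no conversion is justified.
- *A reader might infer that an analysis of FASTeR as an add-on after negative FAST is missing.* Neither objective asks for one, and the 1-in-4 can be read as the conditional rate behind McNemar's discordant pairs.

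**Conclusion.** The point holds as a wrong or at best ambiguous reference term in the SAP, and it should be corrected before analysis. Followed literally, the stated rule understates the sensitivity of both exams and the gain between them by the factor (1-f). It also lowers NPV and raises LR-, while specificity barely moves. For f of 10-30% the illustrative 10-point gain shrinks to 9-7 points and FAST NPV loses 2.6-10.1 points (90.7 - 88.1 and 90.7 - 80.6). These sizes rest on assumed f and prevalence and on no scan-positive subjects among the injured without fluid. The direction follows from the definitions under that last condition.

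The paired test of FAST against FASTeR is not undermined by the reference term. The view matter is an instruction to carry the Primary Objective into the SAP; it is not a second error.

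**What to change.** 1. In the SAP, score both exams against hemoperitoneum present or absent (item 8), accepting only CT or operative confirmation. The restriction has to be written out, because item 8 says imaging in general and item 6c allows ultrasound, which would let ultrasound verify an ultrasound test. Report injury complex (item 7) descriptively. Align the Primary Objective wording, and add hemoperitoneum to the Research Design list of data that every center submits.
2. State in the SAP that the primary estimates and McNemar's test use the FAST RUQ view against the FASTeR RUQ view. State also that the target is any hemoperitoneum, because item 8 records no location and the Primary Objective could be read as fluid located in the RUQ.
3. State in Study Duration whether the 60% and the 1-in-4 are per injured subject or per hemoperitoneum case.

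A secondary comparison of three-view FAST alone with three-view FAST plus FASTeR is optional.

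The cost is wording and a check of the data form. Confirm that item 4 is stored per view, that all centers submit item 8, and that the method confirming hemoperitoneum is recorded, since item 6 records it for the injury complex. No new measurement is listed and patient management is not touched.

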We anticipate a rolling accruement of subjects over a two year period. A sample size calculation (power analysis) was performed to estimate the needed total participant accruement to provide a power of 90% and an alpha of <0.05. Standard FAST should identify up to 60% of subjects with significant intra-abdominal injury. If we assume that the FASTeR will identify hemoperitoneum in 1 of 4 subjects with intra-abdominal injury and previous negative FAST examination, then our needed sample size is 209 subjects. To account for subjects meeting exclusion criteria, we will plan to accrue 250 patients. Given that this sample size calculation was based on estimation regarding the sensitivity of the FASTeR in this patient population, interim analyses regarding primary endpoint will be conducted after 100 subjects have been accrued and again after 200 subjects have been accrued. Subject charts will be reviewed in increments of ten as they are enrolled.

Withdrawal of Subjects

Subjects that are unable to tolerate the position changes described in the protocol will be considered screening failures and will be automatically withdrawn from the study.

Subjects that receive the FASTeR are free to withdraw themselves from the study at any time. They may withdraw from the study by notifying the PI, [name], directly by phone. The option to withdraw and the contact information for [name] are listed on the study information flyer that will given to all subjects.

Quality Control and Quality Assurance

Study data will be collected and managed using REDCap electronic data capture tools. REDCap (Research Electronic Data Capture) is a secure, web-based application designed to support data capture for research studies, providing 1) an intuitive interface for validated data entry; 2) audit trails for tracking data manipulation and export procedures; 3) automated export procedures for seamless data downloads to common statistical packages; and 4) procedures for importing data from external sources (7).

Satellite centers are responsible for getting IRB approval and maintaining their own data integrity as outlined in their respective IRB protocols and applications. The lead center (MRH) will aggregate and analyze deindentified data collected in REDCap.

Ethical Considerations

This study is to be conducted according to US and international standards of Good Clinical Practice, applicable government regulations and Institutional research policies and procedures.

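### The SAP's only comparative test, a McNemar test of accuracy, on its natural reading tests neither sensitivity nor specificity, the two quantities in the primary objective

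*Combined protocol and SAP*

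**What the plan says.** The Primary Objective of the combined protocol and SAP is "To calculate and compare the sensitivity and specificity of detecting hemoperitoneum in the RUQ for the standard FAST and the FASTeR", judged against CT or operative findings. The Secondary Objective adds predictive values, likelihood ratios and a within-subject comparison: "Exam results for individual subjects will be compared to see if there is a significant difference in result accuracy". The Rationale states a joint aim, to "determine the sensitivity and specificity of the FAST and FASTeR, and determine which exam was more accurate in recognizing hemoperitoneum".

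The Statistical Analysis Plan section defines one analysis set: "All subjects who meet inclusion criteria and have complete data available will be used for data analysis". It plans estimates for each exam, "The sensitivity and specificity (with confidence intervals) for detecting hemoperitoneum using the standard FAST or the FASTeR", and then one comparative method, a McNemar's "test will be used to directly compare the accuracy of the FAST and FASTeR results for individual research subjects". It does not give the cells of the 2x2 table, does not assign the test to subjects with or without hemoperitoneum, and mentions no interval for a difference between the exams.

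The Study Duration section bases the sample size on sensitivity. Standard FAST is taken to find up to 60% of subjects with significant injury, and the gain is stated as "If we assume that the FASTeR will identify hemoperitoneum in 1 of 4 subjects with intra-abdominal injury and previous negative FAST examination". This leads to 209 subjects needed and 250 accrued. Interim analyses of the primary endpoint follow at 100 and 200 subjects. The outcome measures record FAST in three views and FASTeR in the RUQ only.

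**The concern.** A paired test suits this design, since each subject has both exams. The question is what the pairs are scored on.

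If each result is scored correct or incorrect and all subjects enter one table, a case found only by FASTeR counts for it and a new FASTeR false positive counts against it, one for one. The quantity tested is then

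prevalence × sensitivity gain − (1 − prevalence) × specificity loss.

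This is neither of the two quantities in the primary objective, and it changes with the case mix enrolled. A real sensitivity gain can be cancelled when prevalence is low. When prevalence is high, a result in favour of FASTeR can coexist with a specificity loss that nobody tested. The interim analyses inherit the same uncertainty about what the primary endpoint's test is.

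**Working it through.** **1. The plan's own figure.** The stated inputs give a gain of 0.25 × (1 − 0.60) = 0.10 among injured subjects. A two-sided paired McNemar calculation with discordance 0.10 against 0, alpha 0.05 and 90% power gives

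n = [1.96 × √0.10 + 1.2816 × √(0.10 − 0.01)]² / 0.01 = 101 reference-positive subjects.

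This is not 209. Values near 209 appear only with inputs the plan does not state, such as reverse discordance of about 0.022 (207). Sidedness, reverse discordance and prevalence are all unstated, so this does not show that 209 is wrong. It does mean that the sample size cannot reveal which table was intended.

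**2. One dataset, three answers.** Take 209 subjects, 63 with hemoperitoneum and 146 without. Let FASTeR alone detect 6 cases and add 6 false positives.
- Sensitivity: 6 v 0, exact p = 2 × 0.5⁶ = 0.031, FASTeR better. Difference 6/63 = 9.5% (Wald 95% CI 2.3 to 16.8).
- Specificity: 6 v 0, exact p = 0.031, FASTeR worse. Difference 6/146 = 4.1%.
- Pooled accuracy: 6 v 6, p = 1.00.

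**3. Power.** Inputs: N = 209 (Study Duration) and a gain of 0.10 (step 1). Assumed, because the documents do not give them: prevalence 25% or 50%, specificity losses of 0 to 3 points, no FAST-positive case missed by FASTeR, and no FAST false positive corrected by it. Per subject, the probability of a pair favouring FASTeR is prevalence × 0.10, and of a pair favouring FAST (1 − prevalence) × loss. Power is found by enumerating the discordant counts and counting rejections in FASTeR's favour at two-sided 0.05.

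| Prevalence | Specificity loss (points) | Net accuracy difference (points) | Power, uncorrected McNemar | Power, exact McNemar |
|---|---|---|---|---|
| 25% | 0 | 2.50 | 77% | 42% |
| 25% | 1 | 1.75 | 27% | 15% |
| 25% | 2 | 1.00 | 9% | 5% |
| 25% | 3 | 0.25 | 3% | 2% |
| 50% | 0 | 5.0 | 99% | 95% |
| 50% | 1 | 4.5 | 86% | 78% |
| 50% | 2 | 4.0 | 68% | 59% |
| 50% | 3 | 3.5 | 51% | 42% |

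McNemar's test among reference-positive subjects has the zero-loss power in every row, because false positives do not enter it. With all discordant pairs in one direction, the uncorrected test rejects at 4 or more pairs and the exact test at 6 or more. The expected number at 25% prevalence is 209 × 0.25 × 0.10 = 5.2, which explains the gap between the two.

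**4. A larger gain.** The Background gives FAST sensitivity as 20 to 60%. At 20% the same 1-in-4 rule gives 0.25 × 0.80 = 20 points. At 25% prevalence, accuracy-test power is then 99, 77, 51 and 31% (exact 95, 68, 42 and 23%) for losses of 0, 1, 2 and 3 points. At 50% prevalence it is at least 98% throughout (exact at least 96%).

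**5. If all 250 were analysable.** With the 10-point gain at 25% prevalence, accuracy-test power is 87.3, 31.8, 10.5 and 3.3%: the same pattern.

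**The case against.** The strongest reply is that the plan names the right family of test and a defined analysis set, and that the authors probably meant to compare the exams within disease status. Much of this stands. A reader might infer that no subject set exists, or that the plan says nothing about how the exams are compared. Neither is so: the SAP fixes a complete-case set and names one paired test. The gap is narrower. That test is not tied to the primary quantities, and no passage states the split.

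A reader might also infer that FASTeR loses specificity. No passage reports this. The 94.7 to 99.6% range in the Background is spread between series of standard FAST and is no evidence about FASTeR. With zero loss the two tests have equal power.

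The power figures also depend on there being no reverse discordance, which would weaken the sensitivity test too. The 10-point gain is borrowed from a 60% figure for standard FAST, which scans three regions. RUQ-only FAST sensitivity is not given, so the RUQ gain could differ.

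Finally, sensitivity and specificity will be reported for each exam with intervals, so a gain would be visible. But separate intervals ignore the pairing and give none for the difference, which is what the objective asks for.

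**Conclusion.** The point holds as a mismatch between objective and test, and it should be fixed. On its natural reading the one planned comparison serves the secondary objective and tests neither primary quantity, and no paired difference has an interval. That much rests on the text alone.

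The size of the harm is conditional. It is nil if FASTeR costs no specificity. With 209 subjects, a 10-point gain and no reverse discordance, a 2-point loss takes power from 77% to 9% at 25% prevalence, but only from 99% to 68% at 50%. With a 20-point gain at 50% prevalence it is negligible. Prevalence, FASTeR specificity and RUQ-only FAST sensitivity are not in the documents, so the figures illustrate the mechanism and do not forecast the result. The documents do not support saying that the trial will miss a true gain.

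**What to change.** - **Primary comparison.** McNemar's test of sensitivity among reference-positive subjects, using the RUQ result of each exam (exact when discordant pairs are few), with a paired 95% CI for the difference, for example Newcombe or Tango. Use this comparison at the interim analyses.
- **Specificity.** Report the paired difference among reference-negative subjects with a paired 95% CI, as estimation. Its McNemar p-value is supportive only, so no second primary test needs alpha. That test is weak: with 209 subjects, losses of 1, 2 and 3 points and no offsetting pairs, power is 7, 38 and 69% at 25% prevalence (exact 0.5, 10 and 33%) and 2, 16 and 38% at 50% (exact 0.1, 2 and 10%). A non-significant result would not show that specificity is preserved.
- **Pooled accuracy.** Keep it as secondary, with the cells of its 2x2 table and the subjects in it defined.

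The cost is a few SAP sentences. FAST by view, FASTeR in the RUQ and confirmed hemoperitoneum are already recorded, so enrolment and data collection do not change. The downside is a smaller denominator for each comparison. The change does not cure a shortage of reference-positive cases, and it leaves error control across the interim looks as a separate matter.
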